8.3.2 REPORTING OF AN ADVERSE EVENT

All AEs and device deficiencies should be reported to Marani Health on the appropriate CRF within 24 hours of awareness. Marani Health will be responsible for device servicing and replacements.

AEs that are not serious but that are notable and could involve risks to subjects will be summarized in narrative or other format and submitted to the IRB per local IRB reporting requirements.

8.3.3 CLASSIFICATION OF AN ADVERSE EVENT

Adverse events will be classified by seriousness, severity, and relationship to study device and protocol procedures. Marani Health will be responsible for device servicing and replacements.

For adverse events, the following guidelines will be used to describe severity.

- **Mild** – Events require minimal or no treatment and do not interfere with the subject’s daily activities.
- **Moderate** – Events result in a low level of inconvenience or concern with the therapeutic measures. Moderate events may cause some interference with functioning.
- **Severe** – Events interrupt a subject’s usual daily activity and may require systemic drug therapy or other treatment. Severe events are usually potentially life-threatening or incapacitating. Of note, the term “severe” does not necessarily equate to “serious”.

8.3.3.1 RELATIONSHIP TO STUDY APPLICATION

All adverse events will have their relationship to study application and protocol procedures assessed by the study staff who examines and evaluates the subject based on temporal relationship. The degree of certainty about causality will be graded using the categories below.

- **Definitely Related** – There is clear evidence to suggest a causal relationship, and other possible contributing factors can be ruled out. The clinical event, including an abnormal laboratory test result, occurs in a plausible time relationship to study application administration and cannot be explained by concurrent disease or other drugs or chemicals. The response to withdrawal of the study application (dechallenge) should be clinically plausible. The event must be pharmacologically or phenomenologically definitive, with use of a satisfactory rechallenge procedure if necessary.
- **Probably Related** – There is evidence to suggest a causal relationship, and the influence of other factors is unlikely. The clinical event, including an abnormal laboratory test result, occurs within a reasonable time after administration of the study application, is unlikely to be attributed to concurrent disease or other drugs or chemicals, and follows a clinically reasonable response on withdrawal (dechallenge). Rechallenge information is not required to fulfill this definition.
- **Potentially Related** – There is some evidence to suggest a causal relationship (e.g., the event occurred within a reasonable time after administration of the study application). However, other factors may have contributed to the event (e.g., the subject's clinical condition, other concomitant events). Although an AE may rate only as "possibly related" soon after discovery, it can be flagged as requiring more information and later be upgraded to "probably related" or "definitely related", as appropriate.
- **Unlikely to be related** – A clinical event, including an abnormal laboratory test result, whose temporal relationship to study application administration makes a causal relationship improbable (e.g., the event did not occur within a reasonable time after administration of the study application) and in which other drugs or chemicals or underlying disease provides plausible explanations (e.g., the subject's clinical condition, other concomitant treatments).
- **Not Related** – The AE is completely independent of study application administration, and/or evidence exists indicating that the event is definitely related to another etiology. An alternative, definitive etiology must be documented by the study staff.

8.3.4 TIME PERIOD AND FREQUENCY FOR EVENT ASSESSMENT AND FOLLOW-UP

The occurrence of an AE may come to the attention of study personnel during study visits and interviews of a study subject presenting for medical care, or upon review by a study monitor.

All AEs will be captured on the appropriate CRF. Information to be collected includes event description, time of onset, study staff's assessment of severity, relationship to study product and protocol procedures, and time of resolution/stabilization of the event. All AEs will be followed to adequate resolution.

8.3.5 EXPEDITED REPORTING REQUIREMENTS

An investigator shall submit to the sponsor and to the reviewing IRB a written report of any unanticipated adverse device effect (UADE) occurring during an investigation according to the IRB's applicable policies and procedures, but in no event later than 10 working days after the investigator first learns of the effect (21 CFR 812.150(a)(1)).

9 STATISTICAL CONSIDERATIONS

9.1 ANALYSIS POPULATIONS

For all analysis populations the Hospital and Antenatal groups will be combined. Additional supportive analyses will be conducted for each study group separately.

The safety analyses will be conducted for the Safety Population defined as the population of subjects who enter the setup process (see Section 1.2, Schema) regardless of evaluability for performance measures.

The Performance Evaluable Population will be the primary analysis population for performance measures and will be defined as the population of subjects who:

- Enter the monitoring phase per Section 1.2, Schema;
- Have at least 1 minute of concurrent data with both devices; and
- Do not have any major protocol violations.

9.2 STUDY ENDPOINTS

9.2.1 PRIMARY PERFORMANCE MEASURES

- Fetal Heart Rate (FHR) as measured by the M•care System versus standard of care CTG device.
- Maternal Heart Rate (MHR) as measured by the M•care System versus the standard of care CTG Pulse Ox.

9.2.2 SECONDARY PERFORMANCE MEASURES

The secondary performance measure is Uterine Contractions (UC) sensitivity as measured by the M•care System versus the standard of care CTG device. Sensitivity is defined as the proportion of UC events identified by standard of care that are simultaneously (e.g., within 30 seconds) identified by the M•care System.

 MARANI	MARANI PRENATAL CONNECTED CARE (M•care) Safety and Effectiveness Study (M•CARE SE Study)	
Protocol Number: MH-001	Revision Number: G	Page 28 of 46

Hypothesis testing for UC sensitivity will only be conducted if the primary performance measures (i.e., equivalence in FHR and MHR) are met.

Additional UC endpoints as measured by the M•care System versus standard of care CTG device, include:

- Positive predictive value (PPV) defined as the proportion of UC events identified by both the M•care System and standard of care out of those that are identified by the M•care System.
- False Positive Rate defined as the proportion of UC events identified by the M•care System that are not identified by the standard of care.

No hypothesis is planned for the PPV and false positive rate endpoints.

9.2.3 SAFETY OUTCOME MEASURES

Incidence of device related and/or protocol procedure related adverse events (AEs) related to the M•wrap study device.

9.3 STUDY SUCCESS CRITERIA

9.3.1 PRIMARY PERFORMANCE GOALS

Study success will be based on the following:

- M•care System limit of agreement (LOA) as compared with CTG within the performance goal of 15 beats per minute (bpm) for FHR.
- M•care System limit of agreement (LOA) as compared with CTG within the performance goal of 10 beats per minute (bpm) for MHR.

9.3.2 SECONDARY PERFORMANCE GOAL

- M•care System UC detection sensitivity with a performance goal of greater than or equal to 80% agreement with CTG.

9.4 STATISTICAL ANALYSIS

9.4.1 GENERAL CONSIDERATIONS

Each recording session will last for a minimum of 60 minutes and no longer than 120 minutes with multiple observations per subject for FHR and MHR and UC events. For analysis of UC events, blinded review will be conducted by two physicians experienced in obstetrics. In the event of discordance, a third blinded reviewer will serve as an adjudicator.

Confidential

Refer to QMS Number: **VAL-PRO-20-0004, Rev G**
DCR-00306, Effective – 14-Dec-2022

Descriptive statistics will include n, mean, median, standard deviation, minimum and maximum for continuous data and n and percentages for categorical data. To account for the correlation among multiple measurements within subjects, MMRM (mixed-effect model repeated measures) statistical methods will be utilized for the primary analyses, with bootstrap resampling methods conducted as a supportive analysis. Unless otherwise specified all statistical tests will be conducted at a 2-sided alpha of 5%.

9.4.2 SUBJECT ACCOUNTABILITY, DEMOGRAPHIC AND BASELINE CHARACTERISTICS

For each analysis population, the number of subjects will be summarized for each accountability status (e.g., consented, screen failed, enrolled, completed study, or withdrawn). Subjects excluded from an analysis population will be provided in a listing including reason for exclusion (e.g., non-evaluable for performance measures, major protocol deviation, etc.).

For this study, enrollment is defined as subjects who enter the Setup phase per Section 1.2, Schema. Subjects who do not meet these minimum criteria will not be considered enrolled and will not be included in any analysis of performance for safety measures.

Demographic characteristics (age, sex, race, ethnicity, height, weight, pre pregnancy BMI) will be summarized using descriptive statistics for each analysis population.

Baseline obstetrical characteristics will be summarized using descriptive statistics for each analysis population, including obstetrical history, appointment or admission type, and belly circumference.

9.4.3 PERFORMANCE MEASURES ANALYSES

Primary Performance Measures Analysis

A comparison between M•care measurement of FHR vs the standard of care reference measurements will be made using methods described below to test the following equivalence hypothesis corresponding to the Success Criteria defined in Section 3.5 of this protocol:

$H_0: \text{Upper 95\% LOA} > 15 \text{ bpm or Lower 95\% LOA} < -15 \text{ bpm}$ vs

$H_1: -15 \text{ bpm} \leq \text{Lower 95\% LOA} \text{ and Upper 95\% LOA} \leq 15 \text{ bpm}$

A Bland-Altman plot of the mean versus the difference will be presented, and the 95% limits of agreement (LOA) calculated together with respective 95% confidence intervals, which will be compared to the equivalence threshold (e.g., performance goal). Both MMRM analysis (primary) as well as bootstrap resampling techniques (supportive) will be conducted to account for the correlation among repeated FHR measurements within subjects. For the MMRM analysis, the mean difference (bias) and its standard deviation will be estimated from the intercept of the model, assuming a compound symmetric correlation

 MARANI	MARANI PRENATAL CONNECTED CARE (M•care) Safety and Effectiveness Study (M•CARE SE Study)	
Protocol Number: MH-001	Revision Number: G	Page 30 of 46

structure, with the 95% LOA and corresponding 95% confidence intervals calculated as defined by Lu 2016.²¹ MMRM analysis provides for valid inference in the presence of data that is missing at random.

In addition, a Deming regression model will be fitted to the FHR values obtained from both devices; the slope (β_1) and intercept β_0) together with respective 95% confidence intervals will be presented. The confidence intervals of the regression parameters will be calculated with bootstrap resampling methodology, to accommodate repeated measurement within subjects. The results will be presented graphically via scatter plot with the line of slope 1 and intercept 0 superimposed.

A comparison between M•care measurement of MHR vs the standard of care reference measurements will be made using the methods described above to test the following equivalence hypothesis Success Criteria defined in Section 3.5 of this protocol:

H_0 : Upper 95% LOA > 10 bpm or Lower 95% LOA < -10 bpm vs

H_1 : -10 bpm \leq Lower 95% LOA and Upper 95% LOA ≤ 10 bpm

Secondary Performance Measures Analysis

A comparison of sensitivity in UC events detected with M•care measurement vs the standard of care will be made using methods described below to test the following hypothesis:

H_0 : Sensitivity $< 80\%$ vs H_1 : Sensitivity $\geq 80\%$

To compare sensitivity (percent positive agreement) in UC events between M•care and standard of care, both MMRM analysis for binary data (primary) and bootstrap resampling techniques (supportive) will be used to account for the correlation among repeated UC measurements within subjects. For the MMRM model, the sensitivity will be estimated from the intercept of the model, presented with corresponding 2-sided 95% confidence interval (e.g., corresponding to a 1-sided alpha 2.5%).

Estimates of false positive rate and PPV in UC events detected with M•care measurement vs the standard of care will be made using both MMRM analysis for binary data (primary) and bootstrap resampling techniques (supportive), to account for the correlation among repeated UC measurements within subjects. For the MMRM model, estimates will be from the intercept of the model, presented with corresponding 2-sided 95% confidence interval.

Primary and secondary performance measures will also be summarized using descriptive statistics for FHR and MHR, and using a 2x2 cross tabulation table for UC events.

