	
At all times, the M•care system shall be considered a research device. In the clinical setting (i.e., not a research-only visit), the M•care system is an adjunct to routine care and not a replacement for routine or urgent care needs. Only the data from the standard of care reference devices will be available to the clinical care team. Data recorded by the M•care system will not be accessible by study team members, thus clinical decisions for all subjects will solely be based on standard of care practices.

Statistical Considerations	
Success Criteria: Study success will be based on the following two primary performance goals: Primary performance goal, FHR The primary performance goal will be met if the 95% confidence interval for the 95% limits of agreement (LOAs) between the M•care System and the standard of care reference device for the primary performance endpoint, FHR are within the performance goal interval of [-15, 15] bpm. Primary performance goal, MHR The primary performance goal will be met if the 95% confidence interval for the 95% limits of agreement (LOAs) between the M•care System and the standard of care reference device for the primary performance endpoint, MHR are within the performance goal interval of [-10, 10] bpm. Secondary performance goal, UC The performance goal for the secondary endpoint, UC, will be met if the lower bound of the 2-sided 95% confidence interval for sensitivity is greater than 80% for M•care as compared to standard of care reference device. Sample Size Justification: A sample size of N=80 evaluable subjects with an average of 60 minutes of comparative device data will provide adequate power to establish equivalence between M•care and standard of care in the primary performance measurements of FHR and MHR, and the secondary performance measurement of UC event sensitivity. It is anticipated that up to 130 subjects from a minimum of 3 sites may be recruited to allow for inability of approximately 30% of subjects to complete the Monitoring Session per the study protocol. Background Mhajna et al reported the mean difference and (95% LOA) [SD] between INVU and standard of care reference CTG for FHR and MHR measurements as -0.30 bpm (-8.84, 8.24) [SD=4.36] and 0.28 (-5.30, 5.86) [SD=2.85], respectively.¹ Furthermore, Hayes-Gill et al² and Mhajna 2021^{3,4} reported positive agreement (e.g., sensitivity) rates vs IUPC in uterine contraction events of 88%.

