3.5 SUCCESS CRITERIA JUSTIFICATION

Fetal Heart Rate (FHR)

The primary performance endpoint is M•care FHR limit of agreement (LOA) within 15 beats per minute (bpm) of FHR measured with cardiotocography. This 15 bpm LOA is a clinically acceptable range to recognize common clinical phenomena including bradycardia, tachycardia, accelerations, and decelerations.⁷ Most FHR clinical phenomena are defined as an increase or decrease of 15 bpm from baseline, which could be detected given a 15-bpm limit of agreement. Clinical practice guidelines state that moderate FHR variability, between 5 and 25 bpm, is considered normal.¹¹ Baseline HR variability can range from 3-12 bpm as measured with standard CTG, and which increases with gestational age.^{7,12} Moreover, FHR calculations derived from CTG have previously been shown to have a high degree of inaccuracy when compared with those derived from fetal ECG-based measurements.⁷ Thus, given the known limitations of CTG, some of variability quantified by the limits of agreement in this study may be due to error in CTG measurements and not M•wrap measurements.

In a study reported by Cohen, et al, the limits of agreement for both FHR and MHR with FSE, abdominal fetal ECG and ultrasound were clinically evaluated.¹³ In this study, the abdominal fetal ECG limits of

agreement (± 1.96 SD) for fECG to FSE was 8.40; -8.72 and for the Doppler ultrasound technique the bias is significantly greater, -2.87, with limits of agreement of (22.65, -28.39)⁷ indicating an even wider interval may be considered clinically insignificant. The FHR performance goal interval of [-15, 15] bpm is based on the clinically significant margin for differences in FHR that have been variously reported in the literature as: >15bpm (e.g., large acceleration)¹⁴, and >25bpm (e.g., marked baseline variability).¹⁵

The mean difference (bias) between FHR measurements with fECG and Doppler methods has been reported as 0.74 bpm with 95% LOA of +/- 12 bpm (e.g., SD= 6.1 bpm) by Reinhard et al¹⁴, and -0.3 bpm with 95% LOA of (-8.84, 8.24) (e.g., SD=4.36) by Mhajna et al.¹ The Monica Health Novii wireless patch system Instructions for Use (107-PT-005-EN rev P) indicates that when comparing the Monica Novii System and the predicate Monica AN24 System, the 95% LOA was -13.7BPM to 14.1 BPM.

Maternal Heart Rate (MHR)

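### FHR and MHR success rests only on limits-of-agreement intervals from a compound-symmetric model; if subjects differ in noise these can be too narrow, and the planned bootstrap has no say

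*Combined protocol and SAP*

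**What the plan says.** The synopsis sets the decision rule: "The primary performance goal will be met if the 95% confidence interval for the 95% limits of agreement (LOAs") for "FHR are within the performance goal interval of [-15, 15] bpm". MHR has the parallel rule, "MHR are within the performance goal interval of [-10, 10] bpm". Testing is at a two-sided 5% level (section 9.4.1), so about 2.5% per limit.

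Section 9.4.3 makes the MMRM primary and the bootstrap supportive: "Both MMRM analysis (primary) as well as bootstrap resampling techniques (supportive) will be conducted to account for the correlation". Bias and SD come from an intercept model with a compound-symmetric "structure, with the 95% LOA and corresponding 95% confidence intervals calculated as defined by" a cited Bland-Altman sample-size paper. Section 9.4.1 repeats the ranking: MMRM for the primary analyses, "with bootstrap resampling methods conducted as a supportive analysis".

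The plan does not state:
- which n or standard error enters the limits-of-agreement (LOA) interval when each subject gives many observations;
- the bootstrap's resampling unit;
- any robust standard error or subject-specific variance;
- what happens if the MMRM and the bootstrap disagree.

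**The concern.** An LOA is bias plus or minus 1.96 SD, so its interval is largely an interval for a variance. Under compound symmetry with a common variance, the within-subject part is treated as known from 80 × 29 = 2,320 degrees of freedom. If noise differs by subject, the information on average noise is closer to 80 units, and the model's standard error is too small. A device whose true LOA sits on the margin could then pass more often than intended.

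FHR and MHR equivalence decide study success and open the test of uterine contraction sensitivity. A bootstrap that resamples whole subjects does not need the common-variance assumption. As written, though, a discordant bootstrap result would not change the conclusion.

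Unequal noise is plausible: the trial pools pre-pregnancy BMI from 15 to 45, and antenatal women with women in early labour or induction. The documents do not quantify it.

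**Working it through.** **Inputs (section 9.5).** N = 80; 30 observations per subject; correlation 0.5; FHR difference −0.3 (SD 4.4); MHR 0.3 (SD 3). Margins are ±15 and ±10 bpm.

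**Formulas.** vb is the variance of subject means, vw the mean within-subject variance, and T = vb + vw × 29/30.
- Interval from the compound-symmetric components (delta method): SE = √(vb/80 + 1.96²·V/(4T)), with V = 2vb²/79 + 2(vw × 29/30)²/(80 × 29).
- Ordinary Bland-Altman: SE = SD·√(1/n + 1.96²/(2(n−1))), with n = 80 or n = 2,400.
- Whole-subject percentile bootstrap.

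**The plan's own figure.** FHR: outer LOA 0.3 + 1.96 × 4.4 = 8.92. Component SE is 0.50, so the interval reaches 8.92 + 1.96 × 0.50 = 9.9; with n = 80 (SE 0.84) it reaches 10.6. MHR: 0.3 + 1.96 × 3 = 6.18, reaching 6.9 (SE 0.34) or 7.3 (SE 0.58). All lie far inside the margins. Simulated power is about 100% for both measures and about 82.5% for contraction sensitivity, which agrees with the stated figure of more than 80%.

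**On the margin.** The total SD that puts the outer FHR limit at 15 is (15 − 0.3)/1.96 = 7.5, so T = 56.25. At correlation 0.5, vb = 28.125 + 28.125/30 = 29.06 and vw = 28.125. Then V = 21.38 + 0.64 = 22.02, and SE = √(0.363 + 0.376) = 0.86.

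Now let only the noise vary, log-normally with log-SD 0.5 (90th/10th percentile ratio of subject SDs 3.6). The variance multiplier has variance e¹ − 1 = 1.72. This adds about 27.19² × 1.72/80 = 15.9 to V, plus about 1.1 from its within-subject sampling term. The true SE becomes about √(0.363 + 3.84 × 39.0/225) = 1.01, while the model still reports about 0.86.

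**Simulated false equivalence.** FHR, bias 0.3 (by symmetry the same as −0.3), correlation 0.5; 20,000 trials per model cell; 1,500 trials with 600 resamples per bootstrap cell.

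| Heterogeneity (log-SD) | Component interval | Whole-subject bootstrap | Bland-Altman, n = 80 |
|---|---|---|---|
| None | 0.8% | 1.1% | 0% |
| Noise only, 0.3 | 1.3% | 1.3% | under 1% |
| Noise only, 0.5 | 2.5% | 2.4% | under 1% |
| Noise only, 0.7 | 5.9% | 4.1% | under 1% |
| Noise and bias spread, 0.3 | 4.4% | 2.8% | under 1% |
| Noise and bias spread, 0.5 | 13.7% | 6.2% | 2.5% |
| Noise and bias spread, 0.7 | 27.2% | 11.7% | 11.9% |

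For MHR, the last three rows are 5.7%, 14.9% and 28.6% (component) against 3.6%, 7.1% and 13.3% (bootstrap).

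Equal-noise rates fall below 2.5% because with so small a bias both limits must pass. With bias 4 bpm, where one limit binds, the equal-noise component rate is 4.4%.

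**Lower correlation.** Noise only, log-SD 0.5: component 9% at correlation 0.25 and 23% at 0.1, against 3.6% and 5.8% for the bootstrap. Over both patterns and log-SD 0.3 to 0.7, the component interval runs from about 3% to 40% and the bootstrap up to about 14%.

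**Formula.** With n = 2,400 in the Bland-Altman formula, equal noise alone gives about 5% at correlation 0.1 and 15.9% at 0.5.

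**The case against.** The strongest objection is that the component interval is not shown to be the plan's interval. Section 9.4.3 defers to a paper, and a Bland-Altman standard error with n = 80 is mostly below nominal. This stands: the size of the problem depends on a formula not in the documents. It does not remove the point, because the candidate readings run from near 0% to about 16% with equal noise.

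Three stronger readings are tempting, and the documents do not support them.
- *A reader might infer that unequal noise as such gives 13 to 29% false equivalence.* At the planned correlation that range needs the spread of subject biases to grow with noise as well, at a log-SD of about 0.5 to 0.7; otherwise it needs a lower correlation than the plan assumes.
- *A reader might take the FHR SDs in section 3.5 as evidence of heterogeneity.* They run from 4.36 to 13.0, the latter from "limits of agreement of (22.65, -28.39"), as (22.65 + 28.39)/3.92. Assigning them to 75% and 25% of subjects gives 23%, 18% and 14% at correlations 0.1, 0.25 and 0.5, against 3 to 5% for the bootstrap. But these are pooled SDs from different comparisons in different studies, not subject-level SDs. Using the two fetal-ECG-against-Doppler SDs (4.36 and 6.1) gives 1.1 to 1.6% at correlation 0.5 and about 4% at 0.1.
- *A reader might infer that the bootstrap would control the error and should decide alone.* It is not nominal under strong heterogeneity, and under the n = 80 reading it would loosen the rule (noise only, log-SD 0.7: 4.1% against under 1%).

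A model-based primary with a supportive bootstrap is also conventional, and section 9.4.5 presents the primary measures by BMI stratum and study group. Neither changes what decides success.

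**Conclusion.** The concern holds in a conditional form. A compound-symmetric interval alone decides FHR and MHR success, and nothing in the rule protects against subjects differing in noise. With an interval built from the variance components and an LOA on the margin, false equivalence at the planned correlation ranges from about nominal to 6% if only noise varies, and from about 4% to 29% if bias spread scales with it. The whole-subject bootstrap is lower wherever the inflation is material, but not fully nominal.

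This rests on assumed heterogeneity, on equal numbers of observations per subject, and on a formula that the plan does not state. At the planned SDs of 4.4 and 3, against margin-edge SDs of 7.5 and (10 − 0.3)/1.96 = 4.9, the trial is far from the boundary. The protection matters if the device agrees less well than planned.

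**What to change.** In sections 9.4.1 and 9.4.3 and the synopsis success criteria:

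1. State that the bootstrap resamples whole subjects with all their observations.
2. State that the FHR (MHR) goal is met only if the 95% confidence intervals of both LOAs, from both the MMRM and this bootstrap, lie within [−15, 15] ([−10, 10]) bpm.
3. State the n or standard error used in the MMRM LOA interval for repeated data.

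Requiring both intervals cannot raise the false-equivalence rate under any reading of the formula, since a trial must pass both. It also settles how disagreement is handled.

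The cost is wording: the bootstrap is already planned, and section 9.5 reports that power was simulated under either method. The rule becomes slightly stricter if subjects differ in noise. Power at the planning inputs stays about 100%. Some excess over nominal remains under the strongest heterogeneity examined.

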9.5 SAMPLE SIZE JUSTIFICATION

A sample size of N=80 evaluable subjects with an average of 60 minutes of comparative device data will provide adequate power to establish equivalence between M•care and standard of care in the primary performance measurements of FHR and MHR, and the secondary performance measurement of UC event sensitivity according to the success criteria and performance goals presented in Statistical Considerations Section 9.3. It is anticipated that up to 130 subjects may be recruited to allow for inability of approximately 30% of subjects to enter the Monitoring Session phase of the study.

 MARANI	MARANI PRENATAL CONNECTED CARE (M•care) Safety and Effectiveness Study (M•CARE SE Study)	
Protocol Number: MH-001	Revision Number: G	Page 32 of 46

Background

Mhajna et al reported the mean difference and (95% LOA) [SD] between INVU and standard of care reference CTG for FHR and MHR measurements as -0.30 bpm (-8.84, 8.24) [SD=4.36] and 0.28 (-5.30, 5.86) [SD=2.85], respectively.¹ Furthermore, Hayes-Gill et al² and Mhajna et al^{3,4} reported positive agreement (e.g., sensitivity) rates vs IUPC in uterine contraction events of 88%.

Power Considerations

In this study, each recording session will last for a minimum of 60 minutes and no longer than 120 minutes yielding an assumed minimum of 30 observations per subject for FHR and MHR, and an average of 3 UC events per subject. FHR and MHR are assumed to be normally distributed, with FHR mean (SD) of -0.3 (4.4), MHR mean (SD) of 0.3 (3). UC sensitivity is assumed to be distributed binary, with UC sensitivity of 90%. For all measurements, the within subject correlation is assumed to be 0.5 and compound symmetric.

Based on these assumptions and simulations with SAS 9.4 statistical software of MMRM and bootstrap resampling analyses as described above in Statistical Considerations Section 9.4, N=80 evaluable subjects will provide greater than 80% power (using either statistical method MMRM or bootstrap resampling) to establish equivalence between M•care and standard of care in each of the primary performance measurements of FHR and MHR and UC event sensitivity according to the success criteria and performance goals presented in Statistical Considerations Section 9.3.

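### Section 9.4.3 takes the SD for the primary limits of agreement from the MMRM intercept, which does not supply the total SD that those limits need

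*Combined protocol and SAP*

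**What the plan says.** Section 9.4.3 makes a compound-symmetric MMRM the primary analysis of FHR. Under it, "the mean difference (bias) and its standard deviation will be estimated from the intercept of the model", "with the 95% LOA and corresponding 95% confidence intervals calculated as defined by" a cited Bland-Altman sample-size paper (reference 21). MHR is analysed by the same methods.

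The decision rule is in the Synopsis (Section 1.1): "The primary performance goal will be met if the 95% confidence interval for the 95% limits of agreement (LOAs") lies within ±15 bpm for FHR, and likewise within ±10 bpm for MHR. Uterine contraction sensitivity is tested only if both are met (Sections 3.3 and 9.2.2).

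Elsewhere the protocol treats LOA as bias ± 1.96 × SD of the individual differences. Section 3.5 cites "95% LOA of +/- 12 bpm (e.g., SD= 6.1 bpm"), and Section 9.5 quotes published SDs beside the LOA that they generate. The planning inputs in Section 9.5 are "yielding an assumed minimum of 30 observations per subject for FHR and MHR", "FHR and MHR are assumed to be normally distributed, with FHR mean (SD) of -0.3 (4.4), MHR mean (SD) of 0.3 (3"), and "For all measurements, the within subject correlation is assumed to be 0.5 and compound symmetric".

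**The concern.** LOA describe the spread of single paired readings. That spread has two parts: differences between subjects and differences within a subject over the session. In a compound-symmetric model both are covariance parameters; neither is part of the fixed intercept.

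The intercept yields the bias and its standard error. Rescaled by the square root of the number of subjects, the standard error becomes the SD of subject means, which leaves out 29/30 of the within-subject variance at 30 readings. Read as a random intercept, it gives a between-subject SD that leaves out all of it. Either substitute makes the LOA too narrow.

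The interval around each LOA is a second gap. The text names within-subject correlation as the reason for using MMRM and a bootstrap, but prints no interval formula, effective sample size or degrees of freedom. Nor does it say that the supportive LOA bootstrap resamples subjects.

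These two quantities settle both co-primary verdicts and, through the testing order, whether contraction sensitivity is tested at all.

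**Working it through.** **1. Which SD the plan uses elsewhere.** Section 9.5, FHR: −0.30 ± 1.96 × 4.36 = −8.85 to 8.25 (printed −8.84, 8.24). MHR: 0.28 ± 1.96 × 2.85 = −5.31 to 5.87 (printed −5.30, 5.86). Section 3.5: 1.96 × 6.1 = 11.96, printed as 12. All three are total SDs.

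**2. What each reading gives at the FHR planning inputs** (bias −0.3, SD 4.4, correlation ρ = 0.5, 80 × 30):

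- Total SD: 4.4. LOA −0.3 ± 8.62 = −8.9 to 8.3.
- SD of subject means: 4.4 × √(0.5 + 0.5/30) = 3.16. LOA −6.5 to 5.9.
- Random-intercept SD: 4.4 × √0.5 = 3.11. LOA −6.4 to 5.8.
- Standard error of the intercept: 4.4 × √((1 + 29 × 0.5)/2400) = 0.354. LOA −1.0 to 0.4.

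**3. Pass rates: method.** The data are balanced and compound-symmetric, with up to 200,000 simulated trials per scenario. A trial passes if the outer 95% bounds of both LOA lie inside the goal. S² is the variance of subject means and MSW the within-subject mean square; total variance = S² + (29/30) × MSW. The plan prints no interval formula, so these forms are assumptions:

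- Independent pairs: Var(LOA) = SD²/2400 + 1.96² × SD²/(2 × 2399).
- n = 80: Var(LOA) = SD²/80 + 1.96² × SD²/(2 × 79).
- Clustered: S²/80 for the bias, plus the uncertainty of the total SD from both mean squares, by the delta method or by MOVER (chi-square limits of the two mean squares, combined).

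**4. Effect of the SD: true FHR LOA exactly ±15** (bias 0, SD = 15/1.96 = 7.65). At ρ = 0.5 the subject-mean SD is 7.65 × 0.719 = 5.50, so the upper LOA is about 10.8. Its upper bound is about 10.8 + 1.96 × 5.50 × √(1/80 + 1.96²/158) = 12.9, well inside 15.

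| ρ | Between-subject SD | Total SD, clustered CI |
|---|---|---|
| 0.3 | about 100% | under 1% |
| 0.5 | 94–96% | 0.2–0.3% |
| 0.7 | 33–36% | under 1% |
| 0.9 | about 3% | under 1% |

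MHR at exactly ±10 behaves the same way at ρ = 0.5. With 60 or 120 readings per subject the between-subject figure is 95–96%. Both limits sit on the margin here and both must pass, so this case does not test whether an interval holds 2.5%.

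**5. Effect of the interval, with the total SD: one limit on the margin.** Bias 3, SD = (15 − 3)/1.96 = 6.12, true upper LOA exactly 15, ρ = 0.5. Nominal pass rate 2.5%.

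| Interval | Pass rate |
|---|---|
| 2,400 independent pairs | about 29% |
| n = 80 | about 0.1% |
| Clustered, delta | about 4% |
| Clustered, MOVER | 2.8% |

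**6. An FHR case from Section 3.5.** With bias 0.74 and SD 6.1 at ρ = 0.5, the true LOA are −11.2 to 12.7, inside the goal. Pass rates: 100% with a between-subject SD; with the total SD, 99.6% (independent pairs), 82–83% (MOVER) and 48% (n = 80).

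**7. Planned devices.** FHR −0.3 (4.4) and MHR 0.3 (3) pass about 100% of the time under every reading above. The stated power above 80% for these endpoints therefore reproduces.

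**The case against.** The sentence can be read as shorthand for an intercept-only model with compound symmetry. The planning SDs and Section 3.5 both suggest that a total SD was meant. This stands: a reader might infer that the analysis will use the wrong SD, but the documents show an instruction that misnames its source, not a decision to use a smaller SD.

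The most extreme version, with the intercept's standard error as the SD, would pass nearly any device. It is implausible: limits of −1.0 to 0.4 bpm would look wrong at once on the required Bland-Altman plot and beside the descriptive SDs. It should carry no weight.

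A reader might also infer that the LOA interval ignores clustering and is too narrow. The documents do not support that. Giving a method by citation is ordinary practice, the source is not available here, and the n = 80 form would err the other way. The direction of any error is unknown.

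Nor does the comparable system in Section 3.5, for which "the 95% LOA was -13.7BPM to 14.1 BPM", show a false pass. Those limits lie inside ±15 and come from a comparison of two fECG systems.

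What remains is that a pass/fail rule for two co-primary endpoints should have one reading. The sentence, followed as written, gives the wrong quantity, and the citation does not change where that sentence says the SD comes from.

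**Conclusion.** The point holds as a specification error in the primary analysis. The intercept cannot supply the SD for LOA, and the sentence disagrees with the total SD used in Sections 3.5 and 9.5.

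The wording defect is certain; its consequences are conditional. With literal coding and a between-subject SD, the false-pass rate at true FHR LOA of ±15 is about 94–96% at the plan's correlation of 0.5. It falls to about 3% at 0.9. With the correct SD, the unprinted interval alone can move the one-limit boundary rate from about 0.1% to about 29%. These figures assume 80 × 30 balanced, normally distributed, compound-symmetric differences and the interval forms listed above.

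A reader might infer that N=80 is too small or that the power claim fails. Neither follows for FHR or MHR, because planned devices pass about 100% of the time under every reading. What is at risk is the verdict on a device whose spread is larger than planned.

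**What to change.** Replace the sentence in Section 9.4.3 with: bias = model intercept; LOA = intercept ± 1.96 × √(between-subject variance + residual variance), both variances taken from the compound-symmetric covariance estimates; 95% CI of each LOA by MOVER on the variance components, or by a bootstrap that resamples whole subjects. Apply it to FHR and MHR. Do not use the plain delta method, which passes about 4% at the one-limit boundary.

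Confirm that the simulations in Section 9.5 used the same SD and interval, and rerun them only if they did not.

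The cost is one sentence and the matching code, plus a possible rerun of the simulations. Data collection and N=80 do not change.
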